3.1.12 Radiographic Progression

Patients must have evidence of radiographic progression as defined below:

• Stratum 1:

o defined as ≥ 25% increase in the product of the greatest perpendicular diameters of the tumor as a whole (solid and cystic component) AND ≥ 0.4 cm increase in each of at least two dimensions of the tumor as a whole OR any new or worsening neurologic/vision deficit in conjunction with a lesser change in the solid or cystic component.

• Stratum 2:

- o For patients more than 6 months following RT (including radiosurgery or P32), progression is defined as a $\geq 25\%$ increase in the product of the greatest perpendicular diameters of the solid component AND ≥ 0.4 cm increase in each of at least two dimensions of the solid component;
- o For patients more than 12 months following RT (including radiosurgery or P32), progression is defined as ≥ 25% increase in each of the product of the greatest perpendicular diameters of the solid tumor AND ≥ 0.4 cm increase in each of at least two dimensions of the solid tumor. Patients demonstrating predominantly cystic progression more than 12 months after RT must show a continued increase in the cystic component on two serial MRI scans performed at least 4 weeks apart

OR re-accumulation of the cyst following one or more cyst aspirations. Patients with progressive neurologic signs and/or symptoms associated with isolated cyst formation or progression are eligible if the neurologic signs and/or symptoms do not improve within 4 weeks of cyst aspiration.

3.1.13 Pregnancy Status:

Female subjects of childbearing potential must not be pregnant or breast-feeding. Female subjects of childbearing potential must have a negative serum or urine pregnancy test. (Pregnancy test must be repeated within 72 hours prior to the start of therapy).

3.1.14 Pregnancy Prevention:

Subjects of childbearing or child fathering potential must be willing to use a medically acceptable form of birth control, which includes abstinence, while being treated on this study.

3.1.15 Informed Consent:

Ability to understand and the willingness to sign a written informed consent document

3.2 Exclusion Criteria

- 3.2.1 Stratum 1 patients: must not have had > 3 surgical debulking procedures/resections.
- 3.2.2 Patients may not have received prior interferon, either systemic or intra-cystic.
- 3.2.3 Patients must not have evidence of metastatic tumor or other cancer.
- 3.2.4 Patients must not be on steroids other than for physiologic replacement.
- 3.2.5 Patients must not have a severe psychiatric illness, including major depression or any previous suicide attempts.
- 3.2.6 Patients must not be on phenytoin, warfarin or methadone due to potential drug interactions.
- 3.2.7 Patients must not have known hypersensitivity reactions, such as urticaria, angioedema, bronchoconstriction, anaphylaxis, Steven-Johnson syndrome, and toxic epidermal necrolysis to interferon alpha or any other products component.
- 3.2.8 Subjects with inability to return for follow-up visits or obtain follow-up studies required to assess toxicity to therapy.

3.3 Inclusion of Women and Minorities

Both males and females of all races and ethnic groups are eligible for this trial.

3.4 Treatment at Primary Institution

All experimental protocol therapy should be dispensed and all imaging studies must be obtained at the primary institution. Laboratory studies, excluding pharmacokinetic and biologic assays, may be performed at a CLIA-certified laboratory of the investigator's choice.

3.5 Criteria to Start Treatment

- 3.5.1 Subjects must start therapy within seven (7) days of registration.
- 3.5.2 Laboratory tests used to assess eligibility must be repeated if therapy starts more than seven (7) days after obtaining labs to assess eligibility. If a test that is repeated after registration and prior to start of therapy is outside the limits for eligibility, it must be rechecked 48 hours prior to the start of therapy. If the recheck is still outside the limits for eligibility, the subject may not receive protocol therapy and will be considered off study.
- 3.5.3 A urine or serum pregnancy test must be repeated and be negative within 72 hours of beginning the study agent for all females of childbearing potential.

4 REGISTRATION PROCEDURES

4.1 General Guidelines

4.1.1 Prior to Consent

Prior to consent the protocol's status should be verified via the PBTC Protocol Status web page, to ensure study is open to accrual.

4.1.2 Informed Consent

Informed consent must be obtained prior to subject registration. Furthermore, consent should be obtained prior to the initiation of any clinical procedures or assessments performed for the purpose of determining protocol eligibility, which would not otherwise be consistent with the institution's standards of clinical practice.

4.2 Registration Process

Subjects must be registered prior to any protocol treatment. Subject registration is only available to authorized personnel using the PBTC automated registration system. The registration procedures are available in the CRA manual, which is posted on the PBTC members' website. The PBTC Protocol Coordinator listed on the protocol cover page for assistance in the registration process.

Reservations may also be made through the registration system providing time to assess the subject's eligibility. Reservations will be held for a maximum of seven (7) calendar days by which time the subject must have been registered on study. The subject's reservation should be canceled as soon as it is determined that the subject is not eligible or that the family/subject has decided not to consent to the trial.

5 TREATMENT PLAN

• Stratum 1: Patients with progressive unresectable or recurrent craniopharyngiomas treated with surgery alone, who have not received radiation therapy. Patients with unresectable craniopharyngiomas (i.e. residual measurable disease following surgical resection) will be enrolled at the time of progression.

• Stratum 2: Patients with progressive or recurrent craniopharyngiomas following radiation therapy.

5.1 Agent Administration

SYLATRON will be administered as a weekly subcutaneous injection for up to 18 courses with 6 injections per course. Six consecutive weeks will constitute one course and subsequent courses will immediately follow, with no break in the administration of the drug. All patients will receive a dose of 1 mcg/kg/week. The patient's actual weight (in kilograms) should be used when calculating the dose of SYLATRON and doses should be re-adjusted if necessary at the time of each clinic evaluation. See Appendix C for the SYLATRON dosage calculation and dosage chart. Patients or parents will be taught to administer the medication in the outpatient setting (see Appendix B for a parent handout on administering subcutaneous injections). Patients or their guardians will keep a diary to document SYLATRON administration (available on the PBTC-039 webpage).

Since constitutional symptoms (e.g., fatigue, myalgias, fever) are generally the most severe after the first few doses, acetaminophen (15 mg/kg up to max dose of 1000 mg) should be given 30 minutes prior to administering the first six doses (first course) of SYLATRON and prior to subsequent doses if needed. For fever that develops after a dose of SYLATRON, Acetaminophen (15 mg/kg up to max dose of 650 mg PO) can be given q 4-6 hours as needed, but should not exceed 75 mg/kg/day for a total dose of up to 3000 mg/day. Acetaminophen can also be alternated with ibuprofen (10 mg/kg up to a max dose of 600 mg) every 6-8 hours as needed. Patients who are on replacement steroids for adrenal insufficiency should receive stress dose steroids for any fever > 101 degrees Fahrenheit (38.3 degrees Centigrade). Please see Appendix D for suggested stress steroid dosing for SYLATRON related fever.

It is recommended that a follow-up call be placed to the patient or parent within 72 hours of the first dose to evaluate for toxicities and review optimal management.

5.2 Criteria for Starting Subsequent Courses

A course may be repeated every 6 weeks if the subject has no evidence of progression and has again met laboratory parameters as defined in Section 3.1.11. If a subject does not meet these parameters at the end of the treatment course, then SYLATRON should be held until parameters meet the eligibility criteria. If the next course is delayed >21 days due to failure to meet laboratory parameters of eligibility criteria or drug-related toxicity, the subject should be taken off protocol therapy.

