3.1.9 Performance Status

Karnofsky Performance Scale (KPS for \geq 16 yrs of age) or Lansky Performance Score (LPS for < 16 years of age) \geq 60 assessed within two weeks prior to registration (See Appendix A)

3.1.10 **Age:**

18 months – 25 years (Minimum weight 20 Kilogram is required to be eligible for the study, since the minimum injection volume of SYLATRON is 0.05 ml, 20 mcg, SQ as suggested by Merck)

3.1.11 Organ Function:

Patients must have evidence of normal organ function as defined by:

- ANC≥ 1000/µl (unsupported)
- Platelets $\geq 100,000/\mu l$ (unsupported)
- Hg \ge 8g/dL (unsupported)
- ALT \leq 2.5 x the upper limit of institutional normal
- Total bilirubin $\leq x$ 1.5 upper limit of institutional normal
- Serum creatinine ≤ 1.5 x the upper limit of normal for age, or calculated creatinine clearance or nuclear GFR ≥ 70 ml/min/1.73 m²

Table 1

| Serum Creatinine for Age/Gender | | | | |
|---------------------------------|-------------------------------------|--------|--|--|
| Age | Maximum Serum Creatinine (mg/dL) | | | |
| | Male | Female | | |
| 1 to < 2 years | 0.6 | 0.6 | | |
| 2 to < 6 years | 0.8 | 0.8 | | |
| 6 to < 10 years | 1 | 1 | | |
| 10 to < 13 years | 1.2 | 1.2 | | |
| 13 to < 16 years | 1.5 | 1.4 | | |
| ≥ 16 years | 1.7 | 1.4 | | |

The threshold creatinine values in this Table were derived from the Schwartz formula for estimating GFR (Schwartz et al. J. Peds, 106:522, 1985) utilizing child length and stature data published by the CDC.

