6 DOSING DELAYS/DOSE MODIFICATIONS

If patients drop below 20 kg during SYLATRON treatment, they can have SYLATRON held for up to 3 weeks for increasing nutrition. If they can gain weight and return to \geq 20 kg, they could restart SYLATRON and not make up lost weeks. This could happen twice before being removed from study.

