6.2 Transaminase Elevations

No delays or dose modifications should be made for grade 1-2 elevation of SGOT/SGPT. For grade 3-4 elevations, the dose modifications below should be followed.

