6.3 Non-hematologic toxicity other than constitutional symptoms

- Subjects who experience a grade 4 non-hematologic toxicity, or subjects who experience grade 2 or higher cardiopulmonary toxicity that is at least possibly-related to SYLATRON should be removed from protocol treatment and should not restart the drug.
- The development of any other SYLATRON related grade 3 non-hematologic toxicity should result in immediate discontinuation of the drug. Following the discontinuation of the drug, patient should be monitored and may restart the drug if following conditions are met:

Subjects who develop grade 3 SYLATRON-related non-hematologic toxicity other than constitutional symptoms should have the drug withheld until the toxicity resolves to grade ≤1. If the toxicity resolves to Grade 1 or better within 3 weeks of discontinuation of SYLATRON, patients may restart therapy at 0.6 mcg/kg/week.

Toxicity that does not resolve within 3 weeks will require the subject to be removed from protocol therapy. If the toxicity recurs at the 0.6 mcg/kg/week dose, the dose should be decreased to 0.3 mcg/kg/week, provided toxicity has decreased to Grades 0-1 within 3 weeks of discontinuation of SYLATRON. Recurrent Grade 3 non-hematologic toxicity following two dose reductions will require the subject to be removed from protocol therapy. No subsequent dose escalations are permitted after dose reduction for non-hematologic toxicity.

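### At a course start, Sections 5.2 and 6.2 give opposite instructions for ALT above 2.5 x ULN that is still grade 2 or lower, and Table 2 schedules no labs at 9-10 of the 17 later course starts that 5.2 gates

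*Combined protocol and SAP*

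**What the plan says.** **Course-start rule.** Section 5.2 sets the condition for each new course: "A course may be repeated every 6 weeks if the subject has no evidence of progression and has again met laboratory parameters", with the limits taken from 3.1.11. If a patient "does not meet these parameters at the end of the treatment course, then SYLATRON should be held" until the limits are met again. "If the next course is delayed >21 days due to failure to meet laboratory parameters of eligibility criteria" or drug-related toxicity, the patient comes off protocol therapy. The ALT limit in 3.1.11 is "2.5 x the upper limit of institutional normal". AST has no limit there.

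**Transaminase rule.** Section 6, headed "DOSING DELAYS/DOSE MODIFICATIONS", contains 6.2: "No delays or dose modifications should be made for grade 1-2 elevation of SGOT/SGPT". It continues: "For grade 3-4 elevations, the dose modifications below should be followed". Section 6.3 then says that patients with a drug-related grade 3 non-hematologic toxicity "should have the drug withheld until the toxicity resolves to grade" 1 or lower, and that grade 4 ends treatment. The grade 2 hold in 6.3 expressly leaves out transaminase elevations.

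**Calendar.** Under 5.1, treatment is a weekly injection in up to 18 consecutive six-week courses with no gap between them. Table 2 (Section 10) places CBC and chemistries, including ALT, bilirubin and creatinine, before course 2 (footnote A), every 12 weeks in courses 2-9 (footnote C), every 18 weeks in courses 10-18 (footnote F), and at end of treatment.

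**The concern.** **ALT.** Section 5.2 makes no exception for transaminases, and 6.2 makes none for course starts. Suppose a patient reaches a course start with ALT above 2.5 x ULN but still grade 2 or lower. A site applying 5.2 holds the drug and stops protocol therapy if the delay passes 21 days. A site applying 6.2 continues dosing. Both are following the protocol. The toxicity summary in 13.3 will tabulate discontinuations due to toxicity, so part of that table could reflect which section a site chose to follow.

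**Lab schedule.** Section 5.2 requires a laboratory check at every six-week boundary, but the calendar does not provide one at every boundary. A site working from the calendar would start many courses of a drug given at home without that check. This point concerns only the laboratory clause of 5.2. The clause on progression does not need a new scan at each start.

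The two points interact. Adding labs before every course without settling the ALT rule would bring the conflict into play at more course starts.

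**Working it through.** The plan states no figure to reproduce here. The check is a comparison of text, followed by a count.

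**1. ALT at a course start**

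| ALT | 5.2 with 3.1.11 | 6.2 and 6.3 | Conflict? |
|---|---|---|---|
| Up to 2.5 x ULN | start the course | no delay | no |
| Above 2.5 x ULN, grade 2 or lower | hold; off therapy if delayed more than 21 days | no delay, no dose change | yes |
| Grade 3-4 | hold | withhold (grade 3) or stop (grade 4) | none over holding |

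The documents do not print the top of grade 2; they only point to CTCAE. The conflict exists for any grade 2 ceiling above 2.5 x ULN. Assuming a ceiling between 3 and 5 x ULN, the band is 3 - 2.5 = 0.5 to 5 - 2.5 = 2.5 x ULN wide.

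**2. Course starts against scheduled labs**

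Inputs: 18 courses of 6 weeks with no gap (5.1) and the Table 2 intervals. Course k starts at week 6(k - 1), so courses 2-18 start at weeks 6, 12, ..., 102. That is 17 starts: 8 for courses 2-9 (weeks 6-48) and 9 for courses 10-18 (weeks 54-102).

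Table 2 does not say where the 12- and 18-week cycles are anchored, so several anchorings were tried. The five below leave no gap longer than 18 weeks.

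| Lab weeks | Starts without labs, courses 2-9 | Starts without labs, courses 10-18 | Without labs | With labs |
|---|---|---|---|---|
| 6, 12, 24, 36, 48, 66, 84, 102 | 18, 30, 42 (3) | 54, 60, 72, 78, 90, 96 (6) | 9 | 8 |
| 6, 12, 24, 36, 48, 54, 72, 90, 108 | 18, 30, 42 (3) | 60, 66, 78, 84, 96, 102 (6) | 9 | 8 |
| 6, 12, 24, 36, 48, 60, 78, 96 | 18, 30, 42 (3) | 54, 66, 72, 84, 90, 102 (6) | 9 | 8 |
| 6, 18, 30, 42, 54, 72, 90, 108 | 12, 24, 36, 48 (4) | 60, 66, 78, 84, 96, 102 (6) | 10 | 7 |
| 6, 18, 30, 42, 60, 78, 96 | 12, 24, 36, 48 (4) | 54, 66, 72, 84, 90, 102 (6) | 10 | 7 |

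Results:
- No scheduled labs: 9/17 = 52.9% to 10/17 = 58.8% of later starts.
- By phase: 3/8 = 37.5% to 4/8 = 50% in courses 2-9, and 6/9 = 66.7% in courses 10-18.
- Scheduled labs present: 7/17 = 41.2% to 8/17 = 47.1%.
- Longest interval between scheduled labs: 18 weeks, or 18 weekly doses.

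Longer gaps do not improve the picture. Running the first cycle to week 48 and resuming at week 72 (a 24-week gap) leaves 10 starts without labs, 7 of them in courses 10-18. A 30-week gap, from week 42 to week 72, leaves 11. Both exceed the calendar's own 18-week interval.

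**3. Interaction**

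Scheduled labs can now expose the ALT conflict at 7-8 of 17 later starts. With labs before every course, that becomes 17 of 17.

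**The case against.** **The sections can be reconciled.** On this view 5.2 governs course boundaries and Section 6 governs toxicity during a course. Blood counts appear to show the same two tiers: 6.4 asks only for a repeat test when ANC is below 1000 and changes the dose below 500, while 3.1.11 requires 1000 for a new course. This is the best argument, but it does not settle the matter. No text confines 6.2 to mid-course events, and 6.4 never says that delays should not be made. The 6-, 12- and 18-week lab times are whole multiples of the course length, so scheduled ALT results would arise mostly at the very starts that 5.2 gates.

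**The wording is advisory.** Both sections say *should*. That softens each rule but does not tell a site which to follow.

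**The band is assumed.** The width of 0.5-2.5 x ULN rests on a ceiling the documents do not give, and the number of patients affected is unknown. Both limits stand. The existence of the conflict needs only a ceiling above 2.5 x ULN.

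**The calendar is not exhaustive.** Section 5.2 itself imposes the check, 3.4 allows local laboratories, and repeat tests under 3.5.2 and 6.4 are also absent from Table 2. A site can therefore comply by ordering extra tests. This stands, and it makes the second point a mismatch between rule and schedule rather than a missing requirement. The webpage forms mentioned in 5.3.1 and 12.1.1 are not available here; they are described as serving data submission.

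**The importance is limited.** The count applies to patients who complete all 18 courses, and nothing inferential changes. Both are correct. The point remains worth fixing because it decides who is held or taken off drug.

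**Conclusion.** Both parts hold.

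- **ALT rule.** Sections 5.2 and 6.2 contradict each other at a course start, for ALT only, above 2.5 x ULN and up to the top of grade 2. This assumes that the grade 2 ceiling exceeds 2.5 x ULN. The frequency cannot be estimated from the documents.
- **Lab schedule.** For a patient who completes 18 courses, 9-10 of 17 later course starts have no scheduled labs under every anchoring examined that respects the 18-week interval. This assumes courses run without delay and lab visits fall on course boundaries.

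This is a matter of safety and consistent conduct that should be corrected. No effect on the primary endpoints, alpha or power is claimed, and 5.4.2 keeps patients who stop treatment without progression in follow-up.

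**What to change.** 1. **Settle the ALT rule first.** Either state in 5.2 that 6.2 governs transaminases, so that grade 1-2 ALT does not delay a course, or make 6.2 subject to the 3.1.11 ALT limit at course starts. The clinical choice is the sponsor's. The cost is one sentence.
2. **Then align 5.2 with Table 2**, in one of two ways:
   - List CBC, ALT, total bilirubin and creatinine before each course, with local laboratories allowed under 3.4. This adds 9-10 routine draws per patient who completes 18 courses (3-4 in courses 2-9 and 6 in courses 10-18) and may lead to more holds.
   - If the 12/18-week taper, which imaging also follows (9.3.3), is deliberate, limit the laboratory gate in 5.2 to scheduled visits. This takes one more sentence and adds no draws, but accepts up to 18 weeks between tests.

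Sample size, alpha and power do not change under either option.

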6.4 Dose Modification for Hematologic Toxicity

Any subject who has an ANC $<1000/\mu L$ or platelet count $<100,000/\mu L$ should have the test repeated within 1 week (prior to the next dose of SYLATRON). The criteria for dose modification are as follows:

- Absolute neutrophil count (grade 4) <500/μL
- Platelets (grade 3) < 50,000/ μ L

Whenever a subject's blood count(s) drop below the criteria shown above, the SYLATRON will be held until the count(s) recover to Grades 0-1 and the dose will be reduced to 0.6 mcg/kg/week. Toxicity must recover to Grades 0-1 within 3 weeks of discontinuation of SYLATRON in order to allow re-initiation of treatment at the reduced dose. Toxicity that does not resolve within 3 weeks will require the subject to be removed from protocol therapy. Should the toxicity recur at the 0.6 mcg/kg/week dose level, a second dose reduction to 0.3 mcg/kg/week should be performed provided the toxicity has decreased to Grades 0-1 within 3 weeks of discontinuation of SYLATRON. If there is again recurrence of hematologic toxicity meeting the above requirements for dose reduction (i.e., following the second dose reduction) treatment with SYLATRON will be discontinued permanently. No subsequent dose escalations will be permitted after dose reduction for hematologic toxicity.

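### For an ALT above 2.5 x ULN that is still grade 1-2, Section 5.2 holds the drug at a course start while Section 6.2 forbids any delay; the link between Sections 5.2 and 6.4 for blood counts is also left unclear

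*Combined protocol and SAP*

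**What the plan says.** **Course starts.** Section 5.2 lets a course be repeated every 6 weeks if there is no progression and the subject "has again met laboratory parameters as defined in Section 3.1.11". Those limits include ANC of at least 1000/µL, platelets of at least 100,000/µL and an ALT no higher than "2.5 x the upper limit of institutional normal". If they are not met: "If a subject does not meet these parameters at the end of the treatment course, then SYLATRON should be held until parameters meet the eligibility" limits. If the delay exceeds 21 days, "the subject should be taken off protocol therapy".

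**Transaminases.** Section 6.2 says: "No delays or dose modifications should be made for grade 1-2 elevation of SGOT/SGPT". Grade 3-4 elevations are sent to the dose modifications that follow it. Section 6.3 allows the drug to be withheld for some persistent grade 2 toxicities, but leaves transaminase elevations out of that rule.

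**Blood counts.** Section 6.4 has two tiers. A subject with ANC below 1000/µL or platelets below 100,000/µL "should have the test repeated within 1 week (prior to the next dose of SYLATRON"). The criteria for dose modification are lower: ANC below 500/µL (labelled grade 4) or platelets below 50,000/µL (labelled grade 3). Below these the drug is held until recovery to Grades 0-1 and restarted at a reduced dose.

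**Timing.** Table 2 in Section 10 schedules blood counts and chemistries before course 2, then every 12 weeks in courses 2-9 and every 18 weeks in courses 10-18.

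**The concern.** Section 5.2 turns entry limits into a rule for holding the drug and, after 21 days, for ending protocol therapy. Section 6 has its own rules for the same laboratory tests. Neither refers to the other, and no text says which governs when both apply to one result.

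Two sites could therefore follow the protocol faithfully and act differently on the same ALT. One would hold the drug and, if the value stayed up, take the patient off therapy. The other would continue at the same dose. That bears on safety handling and on exposure. It also bears on the planned tabulation of dose reductions and discontinuations due to toxicity (Section 13.3, Analysis Plan), because the counts would partly reflect which section a site had read.

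**Working it through.** The plan gives no figure for this point, so there is nothing to reproduce. The check sets the rules side by side.

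**Step 1. Do both rules meet the same result?** A course is 6 weeks. The first scheduled draw precedes course 2. After that, 12 / 6 = 2 courses and 18 / 6 = 3 courses, both whole numbers. If visits are on time, every scheduled on-treatment chemistry and blood count falls at a course boundary, where Section 5.2 applies. Section 6.2 has no timing limit and Section 6.4 applies whenever counts fall, so they apply there too.

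**Step 2. Compare the instructions at a course start.**

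| Result | Section 5.2 with 3.1.11 | Section 6 | Reading |
|---|---|---|---|
| ALT above 2.5 x ULN, still grade 1-2 | hold | no delay, no modification (6.2) | opposite |
| ALT above 2.5 x ULN, grade 3-4 | hold | modification rules apply (6.2, 6.3) | both stop the drug, on different terms |
| ANC 500-999 or platelets 50,000-99,999 | hold | repeat test before next dose; dosing not addressed (6.4) | unclear |
| ANC below 500 or platelets below 50,000 | hold | hold, then reduce (6.4) | both hold, restart terms differ |
| ANC at least 1000 and platelets at least 100,000 | proceed | no action (6.4) | agree |

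The first row concerns ALT (SGPT) only, because Section 3.1.11 sets no AST limit.

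**Step 3. Width of the ALT band.** Section 7.1 names CTCAE version 4.0 for recording adverse events, but the documents do not print its ALT limits. Let grade 3 start at G x ULN, with G an assumption. The band in conflict runs from 2.5 to G, with width max(0, G - 2.5):

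- G = 2.5: width 0, no conflict
- G = 3: 2.5-3 x ULN, width 0.5
- G = 4: 2.5-4 x ULN, width 1.5
- G = 5: 2.5-5 x ULN, width 2.5

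The conflict vanishes only if grade 3 starts at or below 2.5 x ULN.

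**Step 4. Restart terms.** Section 5.2 restarts at the eligibility limits and mentions no dose reduction. Section 6.4 restarts at Grades 0-1 with a reduction. The wording differs; since the limits of Grades 0-1 are not printed, no numerical comparison is made.

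**Step 5. Off-therapy clock.** Section 5.2 uses more than 21 days; Sections 6.3 and 6.4 use 3 weeks, and 3 x 7 = 21. These agree. What differs is which results start the clock.

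**The case against.** The best defence is that Section 5.2 is a stricter gate for starting a course and Section 6 governs what happens within one. For ANC and platelets this largely stands. Section 6.4 sets criteria for dose modification, triggers its repeat test at exactly the entry values, and asks for it before the next dose. A site that holds at an ANC of 800 at a course start breaches nothing in Section 6.4. A reader might infer that Section 6.4 tells sites to keep treating between its two tiers, but it does not say so. What remains is an interface that nobody has spelled out.

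For ALT the defence fails. Section 6.2 expressly forbids delays and makes no exception for course starts, and a Section 5.2 hold is a delay. The statement in Section 5.1 that courses follow without a break settles nothing either way, since Section 5.2 itself provides for delay.

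Three limits should be granted. After course 2, scheduled draws reach only every second course start, then every third. Repeat and unscheduled tests may fall mid-course, where only Section 6 applies. And the documents do not show how often the ALT band is entered: Section 7.1 lists liver damage in more than 20 of 100 recipients without an ALT level, and Section 2.2.3 reports one dose reduction for grade 3 transaminases in the account of 12 patients at this dose, with nothing on lower elevations.

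A reader might also infer that removals under Section 5.2 bias the Stratum 1 endpoint or cost power. The documents do not establish this. An event is progression or death (Section 13.3), patients who stop for other reasons are still followed for progression (Section 5.4.2), and Section 13.4.1 counts a removed patient as a failure only if the primary outcome is not evaluated. A route exists: a removed patient who starts another therapy goes off study (Section 5.5), and later disease status is not collected (Section 5.5.1). Any figure for its effect would need an assumed share of such patients.

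**Conclusion.** Sections 5.2 and 6.2 contradict each other for an ALT above 2.5 x ULN that is still grade 1-2. That conclusion needs only that grade 3 starts above 2.5 x ULN; the width of the band, 0.5 to 2.5 multiples of ULN for G from 3 to 5, rests on the assumed start of grade 3. For ANC 500-999 and platelets 50,000-99,999 the plan is unclear, not contradictory, and the restart wording in Sections 5.2 and 6.4 needs to be aligned or explained. The consequences that can be stated are inconsistent safety handling, exposure and toxicity tabulations across sites. How often this will happen, and whether it reaches the primary endpoint, cannot be determined from the documents.

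**What to change.** Reconcile Section 5.2 with Section 6.2 for ALT, stating both limits on one scale so that they can be compared. State in Sections 5.2 and 6.4 how the course-start limits and the dose-modification limits fit together, including what happens between the two tiers and on what terms treatment restarts. Say which section governs when they differ and which results start the 21-day clock. Which values and rules apply is for the sponsor's medical team to decide. The cost is a wording amendment to Sections 5.2, 6.2 and 6.4, with no new tests, visits or patients.
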